**Overview of Analytic Methods:**

The primary study analyses will adopt an intent-to-treat strategy. Data will be screened for errors using frequency and contingency tables and univariate and bivariate plots before formal analysis. These plots and summaries will allow us to be cognizant of data distribution characteristics before building regression models. To assess indication of self-selection bias, we will compare the demographic characteristics of the participants that agreed to participate in the study to those who were approached, but were not interested in participating.

**Covariate Selection:**

We expect, due to randomization and sufficiently large sample size, that demographic, clinical characteristic, and outcome variables at baseline in the four conditions will not be significantly different. However, we will perform tests for differences (imbalances) on demographic (e.g. age, race, gender) and other potential confounder variables across the four groups. Imbalances may occur in spite of the randomization procedure. If by chance there are important variables significantly out of balance we will add them as covariates in the models.

**Sub study:**

We will interview a set of individuals currently attending one of the recruitment clinics. The study anticipates to conduct at least 3 focus group (of about 8-10 individuals) discussions (FGDs) and stand-alone interviews with 50 participants to learn about the population and ensure our study intervention and study guidance is appropriate for our audience.

**Please note:**

We have increased the total N from 445 to 650, an increase of about 200. This was done for 2 reasons:

1. We previously added a sub study in a prior modification and did not increase the N at that time because enrollment numbers were lower. We have since then consented several individuals to the sub study and we are close to reaching our current N.

2. In the beginning, most individuals we consented for the main smoking study were eligible, however, after consenting approximately 200 individuals, we are having more difficulty consenting individuals who meet eligibility after screening. We may Consent 5 individuals and only 1 is eligible.

We are still keeping the main study at 300 individuals, therefore we are not updating the total N in the consent form. We may need to consent 400 people in order to have 300 eligible.

**2 \* Provide the plan for data analysis. Include in the description the types of comparisons that are planned (e.g., comparison of means, comparison of proportions, regressions, analysis of variance, etc.), which is the primary comparison/analysis, and how the analyses proposed will relate to the primary purposes of the study:**

**Primary Aims:** We will use generalized linear mixed models (SAS, 9.3: Proc GLIMMIX) using a contrast for each post baseline time point to assess the main effects of bupropion vs. placebo (Drug) and PSF vs. SOC (Beh) on smoking cessation. In addition we will assess the interaction of Drug\*Beh and any covariates that were identified above. The test of the hypotheses will be the test of whether the coefficients for the main effects and the interaction are significantly different from 0 based on the likelihood ratio test. If the interaction is significant, we will run additional analyses to explore the simple main effects and will interpret those as opposed to the main effects.

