**1 \* Describe the purpose, specific aims, or objectives of this research. State the hypothesis to be tested:**

Primary Aim 1: Compare bupropion therapy to placebo on rates of 7-day point prevalence abstinence (PPA) at 36 weeks in smokers with HIV/AIDS. We hypothesize that rates of smoking abstinence at week 36 will be higher in those treated with bupropion compared to placebo.

Primary Aim 2: Compare Positively Smoke Free to low intensity, brief counseling on rates of 7-day PPA at 36 weeks in smokers with HIV/AIDS. We hypothesize that rates of smoking abstinence at week 36 will be higher in those treated with Positively Smoke Free compared to brief counseling.

Primary Aim 3: Compare Positively Smoke Free + bupropion to the other two study conditions outlined above on rates of 7-day PPA in smokers with HIV/AIDS at 36 weeks. We hypothesize the effect of Positively Smoke Free with bupropion therapy is greater than the effect of Positively Smoke Free or bupropion therapy alone.

Secondary Aim: Estimate the organizational costs of implementing Positively Smoke Free, bupropion or both. All cost estimates will be appropriately time-discounted and inflation-adjusted. The planned assessment will yield rigorously obtained approximations of total implementation costs at a new site of care.

Exploratory Aim: Explore whether the effect of PSF compared to brief counseling with bupropion is greater than the effect of PSF without bupropion.

Given the critical need for information about the up-front expenses required to implement smoking cessation services in Kenya, we plan to conduct an implementation costs assessment to provide rigorously obtained approximations of total implementation costs of each intervention tested in this trial.

Sub Study:

AIM 1: Develop, culturally adapt and update the PSF intervention in the main study to include educational material about the cancer risk associated with tobacco and alcohol use.

AIM 2: Preliminarily determine the extent the updated PSF syllabus changes awareness of the link between alcohol and tobacco use and cancer.

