**Exploratory Analyses:**

**Other smoking outcomes:** We will use a Generalized Linear Mixed Model (GLMM; Proc MIXED) to assess if the treatment conditions have a significant effect on other smoking outcomes (e.g. number of cigarettes smoked per day) over time. Treatment conditions, time and the interaction of time with the treatment conditions will be included in the model. A random intercept will be used to account for the non-independence of the repeated measures. An unstructured covariance matrix will be employed. Significant effects will be followed up with specific contrast statements.

**Mediation:** We will use Proc Mixed to assess the interventions impact on possible mediating variables for bupropion (craving, withdrawal) and for PSF (self-efficacy, depression, loneliness, substance abuse). Mediators will be assessed at 12 weeks, controlling for baseline. For those variables that are significant we will conduct additional analyses to determine if change in those mediators is related to smoking cessation at 24 weeks. If all conditions are met, we will use the MacKinnon 121 approach to formally assess for mediation of smoking cessation by the targets of the interventions.

**Moderators:** We will assess possible clinical (e.g. depression, smoking severity at baseline, years smoked) and demographic (e.g. age, race) moderators on smoking cessation. We use the analyses described in For Aims 1-3 to assess moderation by including these variables and their interaction with the treatment conditions to the models.

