values in the various study scales. If necessary, we will conduct a sensitivity analysis to investigate how estimates/results change over a range of several plausible assumptions regarding the missing mechanism together with multiple imputations to most accurately capture existent random variability. Multiple Comparisons: We will use the sequential Bonferroni-type procedure for dependent hypothesis tests⁹⁹ to control the false discovery rate (the expected (or on average) proportion of falsely rejected hypotheses) at 5%. Primary Aims: We will use separate logistic regression models (SAS, 9.3: Proc Logistic) at each post baseline time point to assess the main effects of bupropion vs. placebo (Drug) and PSF vs. SOC (Beh) on smoking cessation. In addition, we will assess any covariates that were identified above. The test of the hypotheses will be the test of whether the coefficients for the main effects are significantly different from 0 based on the likelihood ratio test. To assess if the combination of bupropion and PSF is significantly more effective than either of the treatments alone, we will create an indicator variable for these 3 conditions with the combined treatment as the reference. The analysis will proceed as described above.

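### Protocol and SAP give different primary analyses: the protocol states no test of Primary Aim 3 and lets an exploratory interaction displace the main effects, while the SAP's Aim 3 test has two readings

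*Protocol*

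**What the plan says.** **Aims.** Protocol, Justification, Objective, & Research Design, item 1, makes the combination question Primary Aim 3: "We hypothesize the effect of Positively Smoke Free with bupropion therapy is greater than the effect of Positively Smoke Free or bupropion therapy alone". The interaction is listed separately: "Exploratory Aim: Explore whether the effect of PSF compared to brief counseling with bupropion is greater than the effect of PSF without bupropion".

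**Protocol analysis** (Sample Size and Data Analysis, item 2, Primary Aims). The model is "We will use generalized linear mixed models (SAS, 9.3: Proc GLIMMIX) using a contrast for each post baseline time point". The inference rule is "The test of the hypotheses will be the test of whether the coefficients for the main effects and the interaction are significantly different from 0", by likelihood ratio. A positive interaction test triggers a further rule: "we will run additional analyses to explore the simple main effects and will interpret those as opposed to the main effects". No comparison of the combined arm with each single treatment is written down, although the Moderators paragraph looks back to such an analysis: "We use the analyses described in For Aims 1-3 to assess moderation".

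**SAP analysis** (Primary Aims). "We will use separate logistic regression models (SAS, 9.3: Proc Logistic) at each post baseline time point", testing the two main effects only, with no interaction term and no switch to simple effects. For Aim 3, "we will create an indicator variable for these 3 conditions with the combined treatment as the reference", after which the analysis is to run in the same way as for the main effects.

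**Standing of the interaction.** SAP, Power Calculations, calls it exploratory and powers it only for a Cohen's d of .9. Protocol, Sample Size and Data Analysis, item 1, gives it more weight: it plans to distinguish additive from synergistic effects and claims 80% power. The protocol is therefore also divided within itself.

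**The concern.** Both documents present a current confirmatory analysis for the same aims, and the two differ. Neither states precedence in the text available (front matter was removed).

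Two consequences matter. First, Aim 3 is a primary hypothesis whose outcome can depend on which document is opened and on how it is read. That leaves room to choose after the results are known. Second, the protocol lets an interaction that its own aims call exploratory redirect the interpretation of Aims 1 and 2, from comparisons using all participants to comparisons using half of them.

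**Working it through.** **1. The plan's own power figure.** Inputs from Protocol, Sample Size and Data Analysis, item 1: 300 participants, 20% attrition, two-sided alpha .05, 10% vs 25% for the drug, 7% vs 20% for PSF. Per cell: 300 × 0.8 / 4 = 60, so 120 per main-effect level.

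Power = Φ{ [|p1 − p2| − 1.96 √(2p̄(1 − p̄)/n)] / √[(p1(1 − p1) + p2(1 − p2))/n] }

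- Drug, n = 120: (0.150 − 0.0961)/0.0481 = 1.12, power 87%.
- PSF, n = 120: (0.130 − 0.0865)/0.0433 = 1.01, power 84%.

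The stated figure of more than 80% reproduces. The main-effect power is not in dispute.

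**2. What the switching rule substitutes.** Simple effects compare single cells, n = 60:

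- Drug: (0.150 − 0.1360)/0.0680 = 0.21, power 58%.
- PSF: (0.130 − 0.1223)/0.0613 = 0.13, power 55%.

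**3. Aim 3 decision rules compared.** The documents do not give all four cell rates, so four sets without synergy are assumed (placebo+SOC / bupropion+SOC / placebo+PSF / bupropion+PSF):

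- A: 5 / 14.3 / 15 / 35.7%
- B: 7 / 18.4 / 20 / 42.9%, with PSF at 7% to 20% and the drug odds ratio (0.25/0.75)/(0.10/0.90) = 3.0
- C: 7 / 22 / 20 / 35%, additive on the risk scale (a negative interaction on the logit scale)
- D: 7 / 13.1 / 13.1 / 23.1%, odds ratio 2 for each treatment

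Simulated trials had 60 per cell, week 36 only, no covariates and no false-discovery adjustment, with likelihood-ratio tests at .05. The rules were:

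- *SAP, both*: combined arm significantly better than each single treatment (each 1-df statistic above 3.841).
- *SAP, joint*: 2-df test across the three conditions above 5.991.
- *Protocol, additive reading*: both effect-coded main effects significant and positive, with no significant negative interaction.
- *Protocol, interaction reading*: interaction significant and positive.

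| % of trials | A | B | C | D |
|---|---|---|---|---|
| SAP, both: success | 66.1 | 70.9 | 24.7 | 16.2 |
| Additive reading: success | 69.1 | 79.5 | 55.2 | 16.6 |
| Interaction positive | 2.6 | 2.5 | 0.3 | 2.7 |
| SAP, both vs additive: disagree | 30.5 | 25.6 | 37.9 | 21.0 |
| Interaction significant, either direction | 6.6 | 5.8 | 13.1 | 5.9 |

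The joint test is significant in about 31-86% of trials across A-D. It disagrees with the both-comparisons rule in about 16-20%, and with the additive reading in about 25-40%.

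**4. Why the SAP's wording matters.** If only the drug works (10 / 25 / 10 / 25%), the combination is no better than bupropion alone. The joint test, which carries no direction, is still significant in about 62% of trials. Both comparisons succeed in about 2.5%.

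**5. How often the switch fires.** In A, B and D, where there is no logit interaction, the interaction is significant in about 6-7% of trials. In C it is 13%.

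**The case against.** The strongest defence is that the SAP is the specialised document and would ordinarily be followed, and that both texts test the same two main effects by likelihood ratio at the same time points. The protocol's simple effects would also include the combined arm against each single treatment. And item 1 of the protocol's sample-size section does announce an assessment of additive versus synergistic effects.

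Part of this stands. The interaction has some support in the protocol, so its role in the primary analysis is an internal split and not a plain slip. But the simple effects run only after a significant interaction, and to explore, so they are not a stated Aim 3 test. Custom is also not a precedence statement.

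The numbers have real limits. Three of the four cell rates, or all four, are assumed in each set, and the additive decision rule is one construction of a text that gives none. A week-36 logistic model stands in for the protocol's mixed model, without repeated measures, random effects or dropout. The protocol also states no coding for the factors; effect coding is assumed here. These limits affect the size of the disagreement, not the conflict of wording.

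A reader might also infer that the SAP has one clear Aim 3 test and only the protocol is at fault. The SAP text does not support that: a three-level indicator tested like the main effects allows either a joint or a pairwise test.

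**Conclusion.** The two documents give contradictory rules for the primary aims, and this should be fixed. Confidence is high on the text and moderate on the size, which depends on the assumed rates, 60 per cell, week 36 only and no false-discovery adjustment.

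On Aim 3, the protocol states no test and the SAP states one with two readings. The resulting disagreement is between about one trial in six and two in five, depending on the pair of rules compared. On Aims 1 and 2, the switching rule seldom fires without a logit interaction, but when it does it exchanges 120 vs 120 for 60 vs 60 on the strength of a test the SAP powers only for a large effect.

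Two stronger readings are tempting and are not supported. One takes the interaction as the protocol's Aim 3 test, which would give far larger disagreement (15-68% of trials in A-D against the both-comparisons rule). The protocol's aims list separates Aim 3 from the interaction, and a test that is positive in under 3% of trials without synergy cannot serve Aim 3. The other concludes that mixed versus separate logistic models would change the results for Aims 1 and 2. That difference was not quantified, and nothing here shows that it is either large or negligible.

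**What to change.** Before unblinding:

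1. Amend the protocol's Primary Aims analysis to the SAP's logistic main-effects models at each post-baseline time point. Name week 36 as the primary test for Aims 1 and 2 and week 12 as supportive.
2. In both documents, state that Aim 3 compares the combined arm with each single treatment at week 36, and is supported only if both comparisons are significant in favour of the combination.
3. Delete the rule that simple effects replace main effects. Add one drug-by-behavioural interaction model, with simple effects, to the SAP under the Exploratory Aim; the SAP currently contains none.
4. State that the SAP governs, and that its false-discovery family includes the Aim 1-3 tests.

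This is wording only: no new data and no extra participants. There are three costs. The mixed model loses its primary role. A significant interaction no longer redirects the primary interpretation. Requiring both Aim 3 comparisons lowers power to about 16-71% across A-D, against 31-86% for the joint test, in each case before false-discovery adjustment. The last cost is justified because the joint test does not answer Aim 3 as the protocol words it.

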**Exploratory Analyses:**

**Other smoking outcomes:** We will use a Generalized Linear Mixed Model (GLMM; Proc MIXED) to assess if the treatment conditions have a significant effect on other smoking outcomes (e.g. number of cigarettes smoked per day) over time. Treatment conditions, time and the interaction of time with the treatment conditions will be included in the model. A random intercept will be used to account for the non-independence of the repeated measures. An unstructured covariance matrix will be employed. Significant effects will be followed up with specific contrast statements.

**Mediation:** We will use Proc Mixed to assess the interventions impact on possible mediating variables for bupropion (craving, withdrawal) and for PSF (self-efficacy, depression, loneliness, substance abuse). Mediators will be assessed at 12 weeks, controlling for baseline. For those variables that are significant we will conduct additional analyses to determine if change in those mediators is related to smoking cessation at 24 weeks. If all conditions are met, we will use the MacKinnon 121 approach to formally assess for mediation of smoking cessation by the targets of the interventions.

**Moderators:** We will assess possible clinical (e.g. depression, smoking severity at baseline, years smoked) and demographic (e.g. age, race) moderators on smoking cessation. We use the analyses described in For Aims 1-3 to assess moderation by including these variables and their interaction with the treatment conditions to the models.

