Female participants who have the potential to become pregnant will have a pregnancy test during the evaluation phase and approximately monthly during the study (while taking study medication). They will be asked to use acceptable method of contraception during the medication phase of the study (week 1-12). Participants will sign a contraception consent to confirm their agreement (In the baseline packet). Condoms will also be provided at research appointments.

Baseline Interview:

Participants will also complete a series of assessment questionnaires (baseline interview). Vital signs will also be recorded. Only those continuing to meet full inclusion criteria and do not meet exclusion criteria will proceed to randomization and remain in the study. The list of assessments to be completed are located in the study schedule in the Additional Documents section.

Randomization

Study participants who are deemed eligible for the study will complete baseline testing and will then be randomized 1:1:1:1 to four study conditions: (1) Bupropion + PSF; (2) Bupropion + SOC; (3) Placebo + PSF; (4) Placebo + SOC. Participants will be randomly assigned to one of the four conditions using permuted blocks which will randomly vary in size. The research pharmacy will be notified of the drug randomization (Bupropion or placebo). All raters, investigators, and other staff will be blind to treatment assignment except for the dispensing pharmacist. Separate emergency unblinding envelopes for each participant will be kept in a locked cabinet at the dispensing pharmacy in the case of a medical emergency. All participants who are randomized will be taught the correct use of the study medication, and assisted in setting a quit date with the instruction to quit on approximately Day 8 (beginning of Week 2) following one week of medication.

Medication Intervention:

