PSF is an intensive, tailored, social cognitive theory-driven intervention that promotes cessation in PLWH smokers. Its development was guided by previous pilot work characterizing the sociobehavioral drivers of tobacco use in PLWH 40. It is an 8-session program, with session lengths ranging from 45-60 minutes. A syllabus serves as a guide for therapists. The course content has gone through multiple rounds of revision in response to input from intra and extra-institutional experts in HIV and smoking cessation, PLWH smokers, and the ID Clinic community advisory board. Themes of particular relevance to HIV-infected smokers permeate the course content, and the heterogeneity of the PLWH community and how this relates to smoking behaviors (i.e. similarities and differences between drug users, LGBT, and depressed individuals) is highlighted. The "microtargeting" of these subsets of PLWH has received the praise of group participants. An overview of the course content, including tailoring themes, has been previously published. All treatment sessions are audiotaped. If a participant misses an intervention session, we will call him/her to reschedule. If the participant is having difficulty attending some of the sessions in person, we will offer to conduct them over the telephone.

Control Condition

Those randomized to standard of care will receive of standard of care smoking cessation treatment by a trained research assistant at the time of randomization. Participants will be given a quit smoking brochure and brief advice to quit (i.e. < five minutes)

Follow Up Assessment Interviews:

All participants will be re-assessed at approximately week 12 and approximately week 36. Vital signs will also be recorded. All assessments will be administered in a confidential and private location by experienced research assistants who are masked to the results of randomization. The list of assessments to be completed are located in the study schedule in the Additional Documents section.

Participants will also complete a brief visit when they return at week 1, 2, 4, and 8 for their medication refill. All participants will complete vital signs as well as answer a few questions about their medication side effects (if any), medication adherence, their mood and smoking status.

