**1 \* Provide the rationale and sample size calculations for the proposed target population:**

With a total of 300 participants and an estimated 20% attrition, we will have 60 participants per cell in the factorial design. This will provide a total of 120 participants per main effect condition (Drug or Psychosocial Intervention). Meta analyses of bupropion vs. placebo in the general population estimate the effect as an increase in abstinence from 10% with placebo to 25% with bupropion. The effect for PSF compared to SOC without any drug intervention is estimated to be an increase from 7% to 20%. Using a logistic regression model with alpha equal to .05 (two tailed) we will have greater than 80% power to detect these main effects. We will assess whether the combination of PSF and bupropion will have a simple additive effect on smoking abstinence (no interaction) or synergistic effect on smoking cessation (interaction). We will have 80% power to detect a 10% increase in relative abstinence when PSF is compared to SOC without bupropion to PSF compared to SOC with bupropion. Power was calculated using the PASS software. (Version 13, Logistic Regression Procedure.)

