Exploratory Analyses: Other smoking outcomes: We will use a Generalized Linear Mixed Model (GLMM; Proc MIXED) to assess if the treatment conditions have a significant effect on other smoking outcomes (e.g. number of cigarettes smoked per day) over time. Treatment conditions, time and the interaction of time with the treatment conditions will be included in the model. A random intercept will be used to account for the nonindependence of the repeated measures. An unstructured covariance matrix will be employed. Significant effects will be followed up with specific contrast statements. Mediation: We will use Proc Mixed to assess the interventions impact on possible mediating variables for bupropion (craving, withdrawal) and for PSF (self-efficacy, depression, loneliness, substance abuse, and dosage of the PSF intervention (number of sessions completed)). Mediators will be assessed at 12 weeks, controlling for baseline. For those variables that are significant we will conduct additional analyses to determine if change in those mediators is related to smoking cessation at 36 weeks. If all conditions are met, we will use the MacKinnon 100 approach to formally assess for mediation of smoking cessation by the targets of the interventions. Moderators: We will assess possible clinical (e.g. depression, smoking severity at baseline, years smoked, etc.) and demographic moderators on smoking cessation. We use the analyses described for the primary aim to assess moderation by including these variables and their interaction with the treatment conditions to the models

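### Exploratory mediation: step 2 does not say that baseline is in the model, and indirect effects are estimated only after significance screens that inflate them

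*Protocol*

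**What the plan says.** The mediation analysis is in the Protocol under Sample Size and Data Analysis, item 2, Exploratory Analyses, and in the SAP under Exploratory Analyses. It has three steps.

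- Step 1, treatment to mediator: "Mediators will be assessed at 12 weeks, controlling for baseline".
- Step 2, mediator to cessation, only for mediators that were significant in step 1. Protocol: "we will conduct additional analyses to determine if change in those mediators is related to smoking cessation at 24 weeks". SAP: "determine if change in those mediators is related to smoking cessation at 36 weeks".
- Step 3, formal test: "If all conditions are met, we will use the MacKinnon 121 approach to formally assess for mediation". The SAP has the same condition.

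Neither document defines change, lists the covariates of step 2, or gives a significance level for either screen. The named mediators are craving and withdrawal for bupropion, and self-efficacy, depression, loneliness and substance abuse for PSF. The SAP adds a further PSF mediator, the count of sessions completed.

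On timing, the Protocol (Study Procedures, follow-up interviews) says: "All participants will be re-assessed at approximately week 12 and approximately week 36". No week-24 assessment is described.

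**The concern.** Step 1 names its baseline adjustment and step 2 does not. A programmer could therefore fit cessation on week 12 minus baseline with no baseline term. That difference carries the baseline level with its sign reversed, so its slope is not in general the effect of the mediator at week 12. A mediator that truly matters could then fail step 2 and never reach the formal test.

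The second issue does not depend on how change is read. An indirect effect is estimated only when both of its component paths have already passed a screen, so the estimates that get reported are selected for being large.

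This is the plan's only analysis of how the treatments work. The stakes are missed mediators on one side and overstated indirect effects on the other.

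**Working it through.** **Plan's own figures.** The documents give no effect size, correlation, SD or power for mediation. The nearest figure is main-effect power: 300 × 0.80 = 240 evaluable, 60 per cell, 120 per main-effect arm, with stated power above 80%. At 120 per arm and two-sided 0.05, I get 87% for 10% v 25% and 84% for 7% v 20%, so that figure reproduces. I use N = 240 below. Everything about the mediators is an assumption, shown as a range where possible.

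**Step-2 slope if change is unadjusted.** Let the log odds of cessation be k + b1·M12 + b0·M0, with equal SDs σ and correlation r.

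- Cov(b1·M12 + b0·M0, M12 − M0) = (b1 − b0)(1 − r)σ²
- Var(M12 − M0) = 2(1 − r)σ²
- Slope on change ≈ (b1 − b0)/2, whatever r is

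With b1 = 0.5:

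- b0 = 0 (only the week-12 level matters): 0.25, half the true slope.
- b0 = +0.2 (high baseline acts the same way): 0.15.
- b0 = −0.5 (change itself is the driver): 0.50, no bias.

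Large-sample logistic fits (n = 400,000, odds ratio 2.0 per unit of the week-12 mediator, 15.5% abstinence, the mean of the four planned rates) give these ratios of fitted to true slope:

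| Situation | Unadjusted change | Baseline in model |
|---|---|---|
| b0 = 0, equal SDs | 0.46–0.47 | 0.99–1.00 |
| b0 = 0, week-12/baseline SD ratio 0.8–1.3 | 0.16–0.85 | 0.99–1.02 |
| b0 = −b1 | 0.99–1.01 | 0.99–1.01 |
| Whole grid (b0/b1 from −1 to +0.5) | −0.23 to 1.01 | 0.98–1.03 |

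With baseline in the model, change and the week-12 value give the same mediator coefficient.

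**Consequence for step 2.** Simulation of 2,000 trials per setting, 120 v 120, treatment effect on the mediator 0.3 SD, log odds ratio 0.5 per SD, b0 = 0, equal SDs, r = 0.3/0.5/0.7, two-sided 0.05. Ranges cover repeated runs.

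- Mean slope: 0.24–0.25 unadjusted, 0.51 adjusted.
- Step-2 power: 38–41 / 29–30 / 18–20% unadjusted; 77–80 / 69 / 53–54% adjusted.
- Both steps passed: 27–28 / 22 / 17% unadjusted; 53–54 / 51–53 / 48% adjusted.

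**Inflation from the screens, with the slope correctly specified.** Average estimate among trials passing both screens, relative to the true indirect effect (3,000 trials per setting):

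| Treatment effect on mediator (SD) | Log odds ratio per SD | Inflation |
|---|---|---|
| 0.2 | 0.4 | 2.14 |
| 0.25 | 0.3 | 2.25 |
| 0.3 | 0.4 | 1.57 |
| 0.3 | 0.5 | 1.40 |
| 0.4 | 0.5 | 1.20 |

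Repeat runs reached 2.4.

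Hand check of the fourth row at r = 0.5. The step-1 standard error is √(1 − 0.25) × √(2/120) = 0.112, so the expected z is 0.3/0.112 = 2.68 and power is 76%. Given significance, the mean z is 2.68 + 0.307/0.765 = 3.08, an inflation of 1.15. Step-2 power of 69% corresponds to an expected z of 2.46, and the mean given significance is 2.46 + 0.353/0.69 = 2.97, an inflation of 1.21. The product is 1.15 × 1.21 = 1.39. The chance of passing both is 0.765 × 0.69 = 53%, in line with the simulation.

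**The case against.** The strongest reply is that the documents never call the change unadjusted. The sentence before step 2 controls for baseline, and a statistician could reasonably carry that into step 2. If so, the coefficient equals that of the week-12 value and the slope problem disappears. This stands: what the documents show is an omission, not a wrong model.

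A reader might go further and infer that the plan halves the mediator slope, so that most real mediators fail. The documents do not support that.

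- Halving needs unadjusted change, equal SDs and no direct baseline effect. None of these is stated.
- If change itself drives cessation, unadjusted change is the slightly better analysis. At an odds ratio of 2.0 per SD and r = 0.3/0.5/0.7, it misses 1/5/18% of real mediators, against 6/10/25% with baseline in the model.
- Failure also reflects limited power. At an odds ratio of 1.5 with b0 = 0, the adjusted model itself misses 46/55/67%, against 76/81/88% unadjusted.
- Neither document says that failing a screen will be read as evidence against a mechanism.

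A reader might also infer that the two paths refer to different variables, so that their product means nothing. That is too strong. Under randomization, the treatment effect on change and on the week-12 value is the same in expectation, and neither document says which coefficients enter the formal step.

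Finally, the analysis is labelled exploratory, and none of the stated aims rests on it. That limits the weight of the point but does not answer the inflation, which holds on either reading of change.

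**Conclusion.** The point holds in limited form, as an improvement to an exploratory analysis.

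- **Specification gap.** Step 2 should say that baseline is in the model. If it is left out, the slope recovered ranges from −0.23 to 1.01 of the truth over the assumed grid. It is about half when only the week-12 level matters and the SDs are equal. Real mediators can then be missed; how many depends on effect sizes and correlations that the documents do not give.
- **Selection.** Estimating indirect effects only after two screens inflates them by about 1.2 to 2.4 times. This assumes treatment effects on the mediator of 0.2–0.4 SD, log odds ratios of 0.3–0.5 per SD, and both screens at two-sided 0.05.
- **Two textual defects.** The Protocol's 24 weeks conflicts with the SAP's 36 weeks and matches no scheduled assessment. The SAP's sessions-completed mediator has no baseline value, so neither baseline control nor change is defined for it.

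The primary and secondary conclusions are untouched.

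**What to change.** Amend the mediation paragraph in both documents as follows.

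1. Replace step 2 with one logistic model per mediator: cessation at week 36 on the week-12 mediator, its baseline value, Drug and Beh. This is valid whether level or change is the driver.
2. For every prespecified mediator with a baseline measure, report the product of the step-1 treatment coefficient and the step-2 mediator coefficient, with an asymmetric or bootstrap confidence interval.
3. Remove both entry conditions, so that reporting does not depend on the significance of either path.
4. Take sessions completed out of this set, because it has no baseline and no counterpart under SOC. It could be described as a dose-response within the PSF arms.
5. Reconcile the outcome time. The SAP's 36 weeks matches the assessment schedule.

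The cost is wording, one extra covariate per model, slightly less power if change is the true driver, and a longer exploratory table. No new data are needed, because step 1 already uses the baseline and week-12 values.
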